# 10.5 Other events requiring reporting

# **10.5.1 Overdose**

An overdose is defined as a subject receiving a dose of durvalumab + tremelimumab in excess of that specified in the Investigator's Brochure, unless otherwise specified in this protocol.

Any overdose of a study subject with durvalumab + tremelimumab, with or without associated AEs/SAEs, is required to be reported within 24 hours of knowledge of the event to the sponsor and AstraZeneca/MedImmune Patient Safety or designee using the designated Safety e-mailbox. If the overdose results in an AE, the AE must also be recorded as an AE (see Section 10.3). Overdose does not automatically make an AE serious, but if the consequences of the overdose are serious, for example death or hospitalization, the event is serious and must be recorded and reported as an SAE (see Section 10.3). There is currently no specific treatment in the event of an overdose of durvalumab or tremelimumab.

The investigator will use clinical judgment to treat any overdose.

# 10.5.2 Hepatic function abnormality/Hy's Law

Cases where a patient shows elevations in liver biochemistry may require further evaluation and occurrences of AST or ALT  $\ge 3 \times \text{ULN}$  together with total bilirubin  $\ge 2 \times \text{ULN}$  may need to be reported as SAEs. Hepatic function abnormality (as defined in Section 10.1.3.) in a study subject, with or without associated clinical manifestations, is required to be reported as "hepatic function abnormal" within 24 hours of knowledge of the event to the sponsor and AstraZeneca/MedImmune Patient Safety using the designated Safety e-mailbox (for contact information), unless a definitive underlying diagnosis for the abnormality (e.g., cholelithiasis or bile duct obstruction) that is unrelated to investigational product has been confirmed.

- If the definitive underlying diagnosis for the abnormality has been established and is unrelated to investigational product, the decision to continue dosing of the study subject will be based on the clinical judgment of the investigator.
- If no definitive underlying diagnosis for the abnormality is established, dosing of the study subject must be interrupted immediately. Follow-up investigations and inquiries must be initiated by the investigational site without delay.

Each reported event of hepatic function abnormality will be followed by the investigator and evaluated by the sponsor and AstraZeneca/MedImmune.

# 10.5.3 Paternal exposure

Male patients should refrain from fathering a child or donating sperm during the study and for 180 days after the last dose of durvalumab + tremelimumab combination therapy or 90 days after the last dose of durvalumab monotherapy, whichever is the longer time period.

Pregnancy of the patient's partner is not considered to be an AE. However, the outcome of all pregnancies (spontaneous miscarriage, elective termination, ectopic pregnancy, normal birth, or congenital abnormality) occurring from the date of the first dose until 90 days after the last dose should, if possible, be followed up and documented. The patient fathering the child will be asked to provide information.

# 10.5.4 Disease progression

Disease progression can be considered as a worsening of a patient's condition attributable to the disease for which the IP is being studied. It may be an increase in the severity of the disease under study and/or increases in the symptoms of the disease. The development of new or progression of existing metastasis to the primary cancer under study should be considered as diseaseprogression and not an AE. Events that are unequivocally due to disease progression should not be reported as an AE during the study

#### 10.5.5 New cancers

The development of a new cancer should be regarded as an SAE. New primary cancers are those that are not the primary reason for the administration of the study treatment and have been identified after the patient's inclusion in this study.

## 11.0 STATISTICAL METHODS AND SAMPLE SIZE DETERMINATION

# 11.1 Description of analysis sets

# 11.1.1 Safety analysis set

All patients who receive at least 1 dose of study drug will be included in the safety reporting and interim safety monitoring.

# 11.1.2 Efficacy analysis set

To be evaluable for the secondary objectives, a patient needs to receive 2 doses of drug, have immune markers measured, and have at least one follow-up for clinical outcome measures. Patients who do not meet this level of evaluability will be described separately to establish any

trends in patient evaluability and comparability of compliant patients with the intended patient population based on available information.

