## 2.2 Secondary Objective(s)

- To assess the efficacy of durvalumab plus tremelimumab in patients with metastatic castration-resistant prostate cancer.
- To explore immunological changes in peripheral blood and tissue (e.g. peripheralblood cluster of differentiation (CD)4+(Inducible COStimulator (ICOS)+ T cells, CD3 expression in tissue) in response to durvalumab plus tremelimumab in patients with metastatic castration-resistant prostate cancer.

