# 11.2.2 Efficacy analyses

Efficacy of this combination will be measured by PSA progression-free survival (PFS), radiographic PFS, and maximal decline of PSA from baseline. PSA PFS, radiographic PFS, and time to maximal PSA decline will start at the first day of treatment and will be summarized by Kaplan-Meier. The numeric PSA value at maximal decline will be summarized by a boxplot and as a scatter plot of maximal decline by baseline PSA.

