# 11.2.3 Biomarker endpoint analyses

For continuous data, summary statistics including n, mean, standard deviation, median, minimum and maximum or IQR will be computed. Prostatic T cell infiltration pre-and-post biopsy will be described and graphed over time. Differences in either time point compared to baseline will be compared with a t-test or non-parametric alternative. Cox models will be implemented to explore the relationship of treatment combination, prostatic T cell infiltration, and progression-free survival.

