# 11.3 Determination of sample size

The selection of 20 evaluable patients was intended as a pilot sample size with sufficient numbers to establish safety in this population as shown in Table 5 above while providing sufficient numbers for the secondary endpoints. This will allow investigation of a few marker endpoints and establish safety and feasibility of measuring the markers of interest while being able to accrue within 6 months. No formal hypotheses are planned. These patients will form the basis of designing a hypothesis-driven study in the future. However, we can make a statement about what might be detected in secondary endpoints at this sample size. The association between CD3 change and PSA PFS will be explored with a Cox model with CD3 as a continuous measure. Assuming that

75% (80%) of patients will progress by the end of the study, 20 patients will have 80% power to detect a regression coefficient of 0.72 (0.70) at a 2-sided 5% significance level, assuming the change in CD3 has a standard deviation of 1. The regression coefficient of 0.72 (0.70) is equivalent to a hazard ratio of 2.1 (2.0) or a doubling of risk per unit increase in CD3 (Calculations performed in NCSS-PASS 2005). This would hold true for both biomarker and any model of PSA PFS or Radiological/Clinical PFS.

Even if fewer than 20 patients have information available, this is the first look at these measures. Therefore, the descriptive information gathered on biological markers and outcomes, as well as the feasibility of collecting such information in future trials will be valuable.

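### PSA PFS and radiographic PFS run from day 1 but count only patients who later became evaluable; results for all treated patients should stand beside them

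*Combined protocol and SAP*

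**What the plan says.** Section 2.2 makes efficacy a secondary objective: "To assess the efficacy of durvalumab plus tremelimumab in patients with metastatic castration-resistant prostate cancer". Section 11.1.2, which defines the only efficacy set, lays down the condition that governs all such objectives: "a patient needs to receive 2 doses of drug, have immune markers measured, and have at least one follow-up for clinical outcome measures". Section 4.4 gives the same rule, aims for 20 evaluable patients and caps enrolment at 27, so up to 7 treated patients may fall outside the set.

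For those patients the plan provides two things. Section 11.1.1 keeps them in safety: "All patients who receive at least 1 dose of study drug will be included in the safety reporting and interim safety monitoring". Section 11.1.2 adds that "Patients who do not meet this level of evaluability will be described separately", in order to look for "trends in patient evaluability and comparability of compliant patients with the intended patient population based on available information".

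The time origin is in section 11.2.2: "PSA PFS, radiographic PFS, and time to maximal PSA decline will start at the first day of treatment". No efficacy analysis of all treated patients is specified.

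On the biomarker side, section 11.2.3 says "Cox models will be implemented to explore the relationship of treatment combination, prostatic T cell infiltration, and progression-free survival", and section 11.3 says "The association between CD3 change and PSA PFS will be explored with a Cox model with CD3 as a continuous measure". Inclusion criterion 8 (section 4.1) calls for specimens before treatment, after 2 doses and after 4 doses. Section 11.3 does not say which of the two later specimens defines the change.

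**The concern.** A curve that starts on day 1 should include everyone at risk on day 1. Here, membership depends on facts known only later: a second dose, a measured marker and a follow-up. A patient who dies, or who progresses and leaves, before meeting all three conditions drops out of the curve altogether, although his time at risk had begun. Describing him separately discloses the selection but does not put his event back.

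At stake is whether the PFS curves describe the patients treated or a somewhat more favourable subset. Section 11.3 says the study will be the basis for designing a later, hypothesis-driven one, so its PFS rates may be carried forward as planning assumptions.

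A second, conditional matter concerns the Cox model in section 11.3. If CD3 change is read from a specimen taken after some patients already have a recorded PSA PFS event, the covariate is measured after the outcome it is meant to explain.

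**Working it through.** **1. Which events can be lost.** Table 1 puts dose 2 at week 4 and the first on-treatment scan at week 8. A scheduled radiographic progression therefore cannot precede dose 2, and the scan that shows it is itself a follow-up. Progression alone does not exclude a patient: section 4.3 (item 7) requires confirmed progression plus a judgement of no further benefit before treatment stops, and section 6.2.2 allows treatment through progression. What can be lost is an early death, an unscheduled scan, an early PSA event in a patient who then leaves, or any event in a patient without a marker measurement. Patients excluded for toxicity or a missed specimen have no known PFS direction.

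**2. Size for PFS.** Inputs: 20 evaluable and 7 excluded patients (section 4.4). Assumed: 50% of evaluable patients are progression-free at 6 months. Let k of the 7 have events before any evaluable patient does, with the other 7 − k censored before those events. The all-treated Kaplan-Meier value is then

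S = 0.50 × 20/(20 + k).

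- k = 0: 0.50 × 20/20 = 50%
- k = 1: 0.50 × 20/21 = 48%
- k = 2: 0.50 × 20/22 = 45%
- k = 7: 0.50 × 20/27 = 37%

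For scale, the standard error of 50% in 20 patients is √(0.5 × 0.5/20) = 11 points. If instead all 7 were followed and none had failed by 6 months, the figure would be (10 + 7)/27 = 63%, so the direction is not guaranteed.

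**3. The power figure in section 11.3.** For one continuous covariate with SD 1, events needed are D = (1.960 + 0.842)²/β².

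- β = 0.72: D = 15.1, and 15.1/0.75 = 20.2 patients. Power with 15 events is Φ(0.72√15 − 1.96) = 79.6%. HR = e^0.72 = 2.05.
- β = 0.70: D = 16.0, and 16.0/0.80 = 20.0 patients. Power with 16 events is Φ(0.70√16 − 1.96) = 80.0%. HR = e^0.70 = 2.01.

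Both agree with the plan.

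**4. When CD3 is read relative to PSA events.** Assumed: 75% progress by 12 months at a constant hazard, so λ = ln 4/12 = 0.1155 per month, and events are dated at the next 4-weekly PSA visit. An event recorded before a given visit then occurred by the visit before it. The proportion of patients with one is 0% before week 4, 10% before week 8, 19% before week 12 and 27% before week 16. A specimen after dose 2 (given at week 4) would fall around weeks 4 to 8, and one after dose 4 (week 12) around weeks 12 to 16.

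Events left for a landmark model, out of 15:

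- Week 8: 15 − 20 × 0.101 = 13.0, or 15 − 20 × 0.192 = 11.2 if events recorded at the specimen visit are also removed.
- Week 16: 15 − 20 × 0.274 = 9.5, or about 8.1 on the stricter count.

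Power, Φ(0.72√d − 1.96), is about 67–74% at week 8 and 53–60% at week 16.

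**The case against.** The strongest reply is that this hardly matters. The plausible shift of 0 to 5 points is under half a standard error. The route to bias is narrow, as step 1 shows. Eligibility (ECOG 0–1, no narcotics for cancer pain, no liver metastases, life expectancy of at least 52 weeks) makes early deaths unlikely. The plan already promises to describe the excluded patients, at most 7 of them. Safety is the primary objective and counts everyone dosed, and section 11.3 plans no formal hypotheses. All of that stands, and it limits the weight of the point. It does not remove the mismatch between time origin and analysis set, nor supply a PFS estimate for the patients treated.

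The all-treated analysis also recovers less for PSA PFS than for radiographic PFS, because Table 2 lists no PSA after treatment stops. That stands too.

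A reader might infer that the Cox model does not identify its patients. Section 11.3 sizes it on 20 patients immediately after naming 20 evaluable ones, and the evaluability rule covers the immunological objective in section 2.2, so the patient set is reasonably clear. Only the specimen that defines CD3 change is missing. Section 11.2.3 does not mention change at all, and a baseline value would need no landmark.

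A reader might also infer that the CD3 test has a badly inflated error rate. In null simulations (20 patients, 6,000 runs, likelihood-ratio test), a day-1 Cox model rejected in 19–23% of runs, depending on how ties were handled. That required a week-16 specimen and a 1 SD fall in CD3 caused by progression. With a week-8 specimen and a 0.5 SD fall it rejected in about 6–7%, against about 5–6% for a landmark model. The documents give no basis for either fall. Evaluability after 2 doses, and permission to leave combination therapy after two cycles (section 6.2.1), make the 2-dose specimen the likelier basis.

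**Conclusion.** The point holds as a cheap improvement. The PFS curves start on day 1 but leave out treated patients who did not become evaluable, and no all-treated efficacy result is planned. The likely effect is 0 to 5 points on an assumed 6-month PFS of 50%. The 37% figure is a remote bound that needs all 7 excluded patients to fail early. It would be wrong to infer that everyone in the efficacy set is guaranteed event-free to week 8, because evaluability sets no such condition.

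The CD3 point is secondary and conditional. The time point should be named in any case. A landmark matters mainly if the 4-dose specimen is used, and the timing figures rest on an assumed hazard and on a PSA progression rule that the plan does not define. The stated 80% power is not in error. The primary safety analysis is untouched.

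**What to change.** 1. In section 11.2.2, report PSA PFS, radiographic PFS and maximal PSA decline in all patients with at least one dose, beside the evaluable-set results. Censor patients who leave without an event at their last assessment, and state how many have no post-baseline PSA. Keep the evaluable set for the marker analyses.
2. The waiver text in section 8.2.2 indicates that patients have finished the treatment phase. If so, label the all-treated analysis as added later.
3. In section 11.3, name the specimen that defines CD3 change. If any PSA PFS event is recorded before it, add a sensitivity analysis: either a landmark at that specimen, with a rule for events recorded at the same visit, or a time-dependent covariate. Note that both use fewer events and so have less than the stated 80% power.

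The cost is analysis-plan wording; no new data are needed. Section 4.3 follows all subjects for survival, and Table 2 continues scans after stopping for toxicity or symptomatic deterioration. The drawbacks are that PFS may look slightly less favourable, and that PSA PFS for early exits will be censored at the last on-treatment PSA.

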# 11.2 Methods of statistical analyses

# 11.2.1 Primary safety analyses

For the interim safety monitoring described below, an extreme toxicity (TOX) will be defined as any grade 3 or higher adverse event that is possibly, probably, or definitely related to any therapy received on this protocol and occurs within the first 8 weeks of therapy (2 cycles) with one exception. Any grade 3 or higher adverse event that is potentially treatable with steroids will only count as an extreme toxicity if it does not improve to grade 1 or better within 2 weeks of steroid therapy.

At the end of the trial, all adverse events will be tabulated by their CTCAE v4.03 name, counted once at the worst grade and the ultimate attribution within the patient. Exploration of these measures by cycle may also be presented.

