## 3.1 Overview of study design

This is an open-label, single center, Phase II pilot study to explore the link between immunological changes and efficacy of durvalumab (1500 mg IV q4w) in combination with tremelimumab (75 mg IV q4w) for up to 4 doses/cycles each followed by durvalumab 1500 mg IV q4w for up to a total of 8 months [9 additional doses/cycles]) in chemotherapy-naïve men with metastatic CRPC.

This study will enroll approximately 27 patients.

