## **Recommended Adverse Event Recording Guidelines**

Attribution	Grade 1	Grade 2	Grade 3	Grade 4	Grade 5
Unrelated	Phase I	Phase I	Phase I Phase II	Phase I Phase II Phase III	Phase I Phase II Phase III
Unlikely	Phase I	Phase I	Phase I Phase II	Phase I Phase II Phase III	Phase I Phase II Phase III
Possible	Phase I Phase II	Phase I Phase II Phase III			
Probable	Phase I Phase II	Phase I Phase II Phase III			
Definitive	Phase I Phase II	Phase I Phase II Phase III			

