# **10.2** Assessment of relationship

Adverse events will be recorded in the EMR and transferred to Prometheus using a recognized medical term or diagnosis that accurately reflects the event. Adverse events will be assessed by the investigator for severity, relationship to the investigational product, possible etiologies, and whether the event meets criteria of an SAE and therefore requires immediate notification to AstraZeneca/MedImmune Patient Safety.

The following variables will be collected for each AE:

- AE (verbatim)
- The date when the AE started and stopped
- Changes in NCI CTCAE grade and the maximum CTC grade attained
- Whether the AE is serious or not
- Investigator causality rating against the IPs (yes or no)
- Action taken with regard to IPs
- Administration of treatment for the AE
- Whether the AE caused the patient's withdrawal from the study (yes or no)
- Outcome

In addition, the following variables will be collected for SAEs as applicable:

- Date AE met criteria for serious AE
- Date Investigator became aware of serious AE
- AE is serious due to criteria
- Date of hospitalization
- Date of discharge
- Probable cause of death
- Date of death
- Autopsy performed
- Description of AE
- Causality assessment in relation to Study procedure(s)
- Causality assessment in relation to Additional Study Drug

Events, which are unequivocally due to disease progression, should not be reported as an AE during the study.

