# 10.3 Study recording period and follow-up for adverse events and serious adverse events

Adverse events and serious adverse events will be recorded from time of signature of informed consent, throughout the treatment period and including the follow-up period (90 days after the last dose of durvalumab + tremelimumab).

During the course of the study, all AEs and SAEs should be proactively followed up for each subject. Every effort should be made to obtain a resolution for all events, even if the events continue after discontinuation/study completion.

If a subject discontinues from treatment for reasons other than disease progression, and therefore continues to have tumor assessments (per Table 2), drug or procedure-related SAEs must be captured until the patient is considered to have confirmed PD and will have no further tumor assessments.

The investigator is responsible for following all SAEs until resolution, until the subject returns to baseline status, or until the condition has stabilized with the expectation that it will remain chronic, even if this extends beyond study participation.

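### The table of all adverse events conflicts with a recording grid that omits unrelated and unlikely Grade 1–2 events in Phase II, and its single undefined attribution per term can distort related counts

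*Combined protocol and SAP*

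**What the plan says.** Safety and tolerability is the only primary objective (Section 2.1), and Section 3.1 gives the phase: "This is an open-label, single center, Phase II pilot study".

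- **Final table, Section 11.2.1:** "all adverse events will be tabulated by their CTCAE v4.03 name, counted once at the worst grade and the ultimate attribution within the patient". The term *ultimate attribution* is not defined.
- **Recording period, Section 10.3:** "Adverse events and serious adverse events will be recorded from time of signature of informed consent". No grade or attribution limit follows.
- **Data entry, Section 12.3:** adverse events go into Prometheus, again without a limit. Section 10.2 has them recorded first in the EMR and then transferred.
- **Grid in Section 10.0, headed "Recommended Adverse Event Recording Guidelines":** reading across from Grade 1, the first two rows begin "Unrelated Phase I Phase I Phase I Phase II" and "Unlikely Phase I Phase I Phase I Phase II". Phase II thus first appears at Grade 3. The next row begins "Possible Phase I Phase II", so Phase II applies there from Grade 1.
- **Serious events, Section 10.4:** all are reported, whatever the attribution.
- **Causality:** five levels in the grid, a yes/no answer in Section 10.2, and possibly, probably or definitely related in the toxicity definition of Section 11.2.1.

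**The concern.** Two separate faults bear on the main safety table.

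**Capture.** The text promises every adverse event, while the grid leaves out the low-grade events judged unrelated or unlikely. A table built from grid-limited data would carry an all-cause label that is untrue for Grade 1–2. Whether a low-grade event is included would also depend on an open-label attribution.

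**Counting.** Each term yields one grade and one attribution per patient. If the term recurs, these two values may come from different episodes, or one episode may hide another. The table could then misstate how many patients had a related event of that term, including at Grade 3 or higher.

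**Working it through.** The plan gives no figure for this point, so there is none to reproduce. The checks are an enumeration and an illustration from the protocol's own data.

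**1. The grid, read for Phase II.** Five attribution levels × five grades = 25 cells. Phase II is absent from 2 rows × 2 grades = 4 cells: unrelated and unlikely at Grades 1 and 2. No Grade 3 or higher cell is missing.

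**2. Possible size for the any-event rate.** Inputs are from Section 1.4.2, Study D4190C00006, which used this combination: any event 95/102 (93.1%), related event 74/102 (printed as 72.6%), any serious event 56, related serious event 36.

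- Gap = (patients with any event − patients with a recorded event) / 102.
- Upper end: only patients with a related event are recorded. (95 − 74)/102 = 21/102 = 20.6 points.
- Lower end: the 21 patients without a related event may still be captured through a serious event or an unrelated Grade 3 or higher event. Serious events without any related serious event number 56 − 36 = 20 patients. If all 20 are among the 21, serious events alone leave 1/102 = 1.0 point. If the last patient had a non-serious unrelated Grade 3 or higher event, the gap is 0.
- Section 1.4.2 gives no all-cause Grade 3 or higher count for this study, so the position between 0 and 20.6 cannot be fixed. The lower end assumes that serious events reported under Section 10.4 enter the table.

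**3. The counting rule.** Take two episodes of one term in one patient, with different grades, the worst Grade 3 or higher, and the first not fatal. There are 14 ordered grade pairs × 4 related/unrelated combinations = 56 patterns.

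| Reading of *ultimate attribution* | Result |
|---|---|
| Final judgement on the worst-grade episode | 0 of 56 mislabelled |
| Attribution of the last episode | 10 of 56 mislabelled: 5 toward related, 5 toward unrelated |
| Strongest attribution | 14 of 56 mislabelled, all toward related |

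The first reading has its own loss. Where the worst episode is unrelated and the other is related (14 grade pairs × 1 = 14 patterns), the related episode disappears. In 4 of these 14, both grades are 3 or higher, so a related Grade 3 or 4 episode is lost.

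The two faults interact. Under the grid, a later unrelated Grade 1 or 2 episode is not recorded and cannot overwrite an earlier related Grade 3. Of the 5 last-episode patterns that shift toward unrelated, only related Grade 4 followed by unrelated Grade 3 then survives. The 5 that shift toward related all remain.

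These are logical patterns, not expected frequencies; the documents give no recurrence rates. In every reading the grade is correct and only the attribution, or a hidden episode, is at issue. One patient weighs 1/27 = 3.7 points at full enrolment, which says nothing about how often this happens.

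**4. The toxicity stopping rule.** An extreme toxicity must be Grade 3 or higher and at least possibly related. None of the 4 missing cells meets either condition. The once-per-term rule is stated for the end-of-trial table, not for the monitoring.

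**The case against.** The strongest reply is that nothing is definitely excluded. The grid is only recommended, events are first recorded in the EMR, and serious events are reported whatever their attribution. Recording by tier is a legitimate choice for a small Phase II study. A natural reading of the counting rule is the final judgement on the worst-grade event, which mislabels nothing. All of this stands as a limit on the point. It does not tell staff which recording rule to follow, and the natural reading still loses related episodes that lie below the worst grade.

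Stronger readings are tempting, but the documents do not support them:

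- *All-cause incidence will be understated.* This holds only if the grid is followed, and the text does not settle that.
- *The gap is 9.6 to 44.9 points.* The ATLANTIC figures in Section 1.4.2 suggest this: any event 264/303 = 87.1%, against between 128/303 = 42.2% and (128 + 107)/303 = 77.6% recorded. But that study is durvalumab monotherapy in lung cancer, and the sum ignores its 94 patients with serious events. Since 128 + 107 + 94 = 329 exceeds 264, the minimum there is also 0.
- *Grade 3 or higher events are moved or lost from the any-cause count.* No reading changes a grade, and the grid drops none of these events.
- *The related Grade 3 or higher rate is the main result.* No section names it so; Section 11.3 rests its safety claim on the monitoring characteristics in Table 5.
- *Five-level causality must be collected.* The toxicity definition and the legible part of the grid need only a split between unlikely and possible. A yes/no answer gives that once yes is defined.

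**Conclusion.** The contradiction on capture is real and unresolved. If the grid governs, the table promised in Section 11.2.1 is not all-cause for Grade 1–2. On the combination data in Section 1.4.2, the any-event rate could be understated by 0 to about 20.6 points. That range comes from a lung cancer population and is an illustration, not a forecast. All-cause Grade 1–2 rates for single terms would also be affected, but the documents do not allow that to be sized.

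The counting rule is a second, independent weakness. The last and strongest readings can mislabel the attribution of a Grade 3 or higher event; the worst-episode reading drops a lower-grade related episode. Either needs a term to recur in one patient with different attributions, at a frequency that the documents do not give.

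The trial's safety monitoring is sound on this point. The final table should still be corrected, because it reports the only primary objective.

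**What to change.** 1. Reconcile the Section 10.0 grid with Sections 10.3, 11.2.1 and 12.3, so that one recording rule applies to this trial. If the grid is kept, restate Section 11.2.1: all-cause rates for Grade 3 or higher and for serious events only, and Grade 1–2 rates labelled as at least possibly related.
2. Replace the single count with two tables, each counting a term once per patient: worst grade regardless of attribution, and worst grade among episodes finally judged at least possibly related. The term *ultimate attribution* is then no longer needed.
3. State in Section 10.2 that a causality answer of yes means possible, probable or definite.

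The cost is wording and one extra table. If the conflict is resolved by recording everything, some low-grade data entry is added for at most 27 patients; if the table is relabelled instead, none is.
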